13.7 Analysis of Secondary Endpoints

OS is defined as the time from treatment onset to death. For events that have not occurred by the time of data analysis, times will be censored at the last contact at which the participant was known to be progression-free for PFS, or the last time the participant was known to be alive for OS. PFS and OS will be estimated using the Kaplan-Meier method (Kaplan, 1958) and 90% confidence intervals for PFS and OS will be reported. Log-rank test (Mantel, 1966) will be performed to test the difference in survival between groups. Regression analyses of survival data based on the Cox proportional hazards model (Cox, 1972) will be conducted on PFS or OS. The proportional hazards assumption will be evaluated graphically and analytically, and regression diagnostics (e.g., martingale and Shoenfeld residuals) will be examined to ensure that the models are appropriate.

NOTE: With Protocol Version 15MAY2024, further long-term follow-up is being terminated.

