4. REGISTRATION PROCEDURES

4.1 General Guidelines for DF/HCC Institutions

Institutions will register eligible participants in the Clinical Trials Management System (CTMS) OnCore. Registrations must occur prior to the initiation of protocol therapy. Any participant not registered to the protocol before protocol therapy begins will be considered ineligible and registration will be denied.

An investigator will confirm eligibility criteria and a member of the study team will complete the protocol-specific eligibility checklist.

Following registration, participants may begin protocol therapy. Issues that would cause treatment delays should be discussed with the Overall PI. If a participant does not receive protocol therapy following registration, the participant's registration on the study must be canceled. Registration cancellations must be made in OnCore as soon as possible.

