5.6 Duration of Follow-Up

Participants will follow-up at approximately 4 weeks for an end of study clinic visit after the last dose of study drug whenever possible. If an in-person visit is not possible, the participant will be contacted by phone. Immune mediated event surveillance will be conducted approximately 100 days after the last dose of study treatment via telephone. Otherwise, ongoing long-term follow-up will be accomplished by phone for all participants. Participants will be followed approximately every three months until death.

In addition to the follow-up schedule above, participants removed from protocol therapy for unacceptable adverse event(s) will be followed until resolution or stabilization of the adverse event.

In participants who come off trial for a reason other than progressive disease, if possible during the follow-up period, scans should be performed every 8 weeks or 2 months to evaluate for disease progression, until the participant has disease progression or dies or starts a new systemic therapy.

NOTE: With Protocol Version 15MAY2024, further long-term follow-up is being terminated.

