11.1.6 Overall Survival, Progression-Free Survival, Time-to-Progression

Overall Survival: Overall Survival (OS) is defined as the time from randomization (or registration) to death due to any cause, or censored at date last known alive.

Progression-Free Survival: Progression-Free Survival (PFS) is defined as the time from randomization (or registration) to the earlier of progression or death due to any cause. Participants alive without disease progression are censored at date of last disease evaluation.

Time to Progression: Time to Progression (TTP) is defined as the time from randomization (or registration) to progression, or censored at date of last disease evaluation for those without progression reported.

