13.6 Analysis of Primary Endpoints

For the analysis of the primary endpoint (PFS_{12 weeks}), we will provide respective point estimate along with 90% confidence interval for each of the combinations. PFS is defined as the time from baseline disease evaluation to either disease progression as defined by RECIST or death from any cause, whichever occurs first. For events that have not occurred by the time of data analysis, times will be censored at the last contact at which the participant was known to be progression-free. Log-rank test (Mantel, 1966) will be performed to test the difference in survival between groups. Regression analyses will be conducted of survival data based on the Cox proportional hazards model (Cox, 1972). The proportional hazards assumption will be evaluated graphically and analytically, and regression diagnostics (e.g., martingale and Shoenfeld residuals) will be examined to ensure that the models are appropriate.

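### Sections 13.6 and 13.7 censor PFS at last contact but 11.1.6 at last disease evaluation; the contact rule can push Kaplan-Meier PFS upward, and the PFS and OS start dates also conflict

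*Combined protocol and SAP*

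**What the plan says.** **PFS censoring.** Section 11.1.6: "Participants alive without disease progression are censored at date of last disease evaluation". Section 13.6: "times will be censored at the last contact at which the participant was known to be progression-free". Section 13.7 repeats the contact rule: "times will be censored at the last contact at which the participant was known to be progression-free for PFS". No section ranks one above the other.

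**Follow-up after treatment (5.6).** There is a visit about 4 weeks after the last dose, by phone if need be, and an immune-event call at about 100 days. "Otherwise, ongoing long-term follow-up will be accomplished by phone for all participants", about every three months until death. Participants who stop for a reason other than progression are to have scans every 8 weeks, but only where possible, and these end at progression, death or new systemic therapy.

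**PFS start.** Registration in 11.1.6 (its alternative, randomization, does not exist in this trial), study enrollment for the 12-week endpoint in 13.1, and the baseline scan in 13.6: "PFS is defined as the time from baseline disease evaluation to either disease progression as defined by RECIST or death from any cause".

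**OS start.** Section 11.1.6: "Overall Survival (OS) is defined as the time from randomization (or registration) to death due to any cause". Section 13.7: "OS is defined as the time from treatment onset to death". Section 4.1 fixes the order of the two dates: "Registrations must occur prior to the initiation of protocol therapy".

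**Use.** PFS and OS are to be reported by Kaplan-Meier with 90% confidence intervals (13.1, 13.7). Log-rank and Cox analyses are also planned (13.6, 13.7).

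**The concern.** RECIST progression is established by a disease evaluation: imaging or, for superficial lesions, caliper measurement (11.1.3). A phone call supplies neither. The plan foresees calls that continue when scans are missing or have ended. If such a call counts as progression-free contact, the participant stays in the risk set over a period in which progression could have happened unseen. Deaths in that period would still be recorded as PFS events, but progressions would not, so the hazard is understated.

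The trial is uncontrolled, and its rationale leans on historical PFS figures (2.3, 2.4). Two written rules allow two curves from the same data, and the looser one favours the treatment. The log-rank and Cox analyses use the same times and carry the same error. The conflicting start dates shift whole PFS and OS times by an amount that depends on which section the analyst follows.

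**Working it through.** **1. The plan's own figure.** No figure is stated for the Kaplan-Meier analyses. The nearest is the 12-week rule in 13.2: at least 9 of 19, 30% against 60%, stated power 91%, one-sided 10%. Exact binomial: P(X >= 9 | n = 19, p = 0.60) = 0.9115 and P(X >= 9 | n = 19, p = 0.30) = 0.0839. A cut-off of 8 would give 0.182, so 10% is the nominal ceiling. The figure reproduces. Under 13.1 a missing 12-week scan is a failure, so the censoring rule does not enter this decision.

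**2. Direction.** Each Kaplan-Meier factor is 1 - d/n at an event time. Moving a censoring date later leaves every d unchanged and can only raise n. No factor falls, so the contact curve is never below the evaluation curve. In 18,000 simulated arms there were no exceptions.

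**3. A constructed arm of 19.** Events: 4 at week 6, 3 at week 12, 3 at week 18, 3 at week 24, 2 at week 36. Four participants have last scans at weeks 6, 6, 12 and 12, and a call 13 weeks later (weeks 19, 19, 25, 25).
- Evaluation rule, week 24: 15/19 x 10/13 x 5/8 x 2/5 = 0.152.
- Contact rule, week 24: 15/19 x 12/15 x 9/12 x 4/7 = 0.271.
- Week 12: 0.607 against 0.632.

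This shows the mechanism; it is not a forecast.

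**4. Simulation, one call.** From the documents: 19 per arm, 12-week rates of 30% and 60% (13.2), scans every 6 weeks to week 24 and then every 12 weeks (11.1). Assumed: exponential PFS, 10%, 20% or 30% ending scans without progression at a uniform time in weeks 6-36, and one call 13 weeks after the last scan. There were 3,000 arms per setting. Mean Kaplan-Meier PFS, evaluation rule / contact rule:

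| True 12-week rate | Early stop | Week 12 | Week 24 | Week 36 |
|---|---|---|---|---|
| 30% | 10% | 0.300 / 0.306 | 0.087 / 0.098 | 0.027 / 0.034 |
| 30% | 20% | 0.298 / 0.307 | 0.089 / 0.109 | 0.029 / 0.044 |
| 30% | 30% | 0.299 / 0.314 | 0.088 / 0.120 | 0.031 / 0.056 |
| 60% | 10% | 0.599 / 0.602 | 0.363 / 0.374 | 0.214 / 0.228 |
| 60% | 20% | 0.597 / 0.604 | 0.354 / 0.379 | 0.215 / 0.244 |
| 60% | 30% | 0.599 / 0.609 | 0.358 / 0.394 | 0.214 / 0.259 |

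Differences: 0.3-1.5 points at week 12, 1.1-3.6 at week 24, 0.7-4.5 at week 36. The evaluation rule stays within 0.5 points of the complete-data curve. The typical median was the same under both rules (12 and 18 weeks).

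**5. Simulation, extreme case.** Assumed: median PFS 2.6 months (the phase III eribulin figure in 2.3), 15% or 30% stopping by week 24, none of them scanned again, and last contact 4, 14 or 26 weeks after stopping. Week-24 PFS is 22.9% by the evaluation rule, against 24.0-29.0% (15% stopping) or 25.2-35.5% (30% stopping) by the contact rule. The largest gap is 35.5 - 22.9 = 12.6 points.

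**6. Start dates.** Registration precedes treatment, so OS from treatment onset is shorter than OS from registration by that gap. Its length is not stated; it is probably days. Baseline scans fall within 2 weeks before therapy (section 10; 11.1.3 has a looser outer limit of 4 weeks). PFS from the baseline scan is therefore longer than PFS from registration, by up to about 2 weeks, where the scan comes first.

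**The case against.** **The wording may already require an evaluation.** Sections 13.6 and 13.7 speak of a contact at which the participant was known to be free of progression, and 13.6 ties progression to RECIST. A strict reader would say that a phone call cannot supply that knowledge. This is fair: the inflation is conditional. But neither section asks for a disease evaluation, and 11.1.6 uses a different term, so the looser reading is open.

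**Events are not found only on scans.** Deaths count and are followed by phone, calipers are allowed (11.1.3), and 5.5 tells investigators to weigh clinical condition. This stands. The gap concerns unseen progression only.

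**The large figure is a worst case.** This also stands. Section 5.6 asks for 8-weekly scans in exactly these participants, and 5.3 lets someone who stops one drug continue on the other. In the extreme model with contact at 26 weeks, 83% of those censored at contact had already progressed (about 65% at 14 weeks), so the contact would have to miss most progressions.

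**A reader might infer that the median moves up by one scan visit.** The documents do not support this. It appears at medians of 2.6 and 4.0 months (5 of 6 scenarios each) because true survival there is just under 50% at a scan: 47.9% at week 12 and 48.8% at week 18. At 2.3 and 3.0 months it moves in 0 of 6, at 3.5 in 2 of 6, and at 4.5 in 1 of 6.

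**Nothing decisive rests on it.** The go/no-go rule is untouched, the curves are descriptive, and PFS beyond 12 weeks is not a listed secondary objective. Correct, and this limits the weight of the point. The curves and intervals are still planned reporting.

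**Long-term follow-up has been ended by the May 2024 version.** That stops further calls. It does not say which rule applies to contacts already recorded.

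**Conclusion.** The plan holds two incompatible PFS censoring rules and does not say which governs. The contact rule can only raise the Kaplan-Meier estimate, and it does so if contacts without a disease evaluation are accepted as progression-free. With 10-30% ending scans early and one call 13 weeks after the last scan, the shift is about 0.3-1.5 points at week 12 and 1-4 points at week 24. About 13 points at week 24 needs 30% stopping, no later scan in any of them, and contact 26 weeks on. The stopping shares, their timing and the contact pattern are assumptions.

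A reader might infer that the trial's conclusion is at risk. It is not: a missing 12-week scan counts as failure under 13.1, whatever the censoring rule. No general shift in the median is claimed.

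The start-date conflicts are real but small: probably days for OS and up to about 2 weeks for PFS. They act in opposite directions, because the 13.7 start shortens OS while the 13.6 start lengthens PFS where the scan precedes registration.

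**What to change.** Wording only, settled before any curves are reported:

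- In 13.6 and 13.7, censor PFS at the date of the last adequate disease evaluation without progression, as in 11.1.6. Count imaging and the clinical measurement that 11.1.3 permits. If there is no evaluation after baseline, censor at the time origin.
- Keep the date last known alive as the censoring date for OS only.
- Use one time origin, registration as in 11.1.6, for PFS and OS in 11.1.6, 13.1, 13.6 and 13.7. Leave the 13.1 failure rule for a missing 12-week scan as it is.

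Cost: no new data, visits or participants. Censoring comes slightly earlier, so intervals widen somewhat in the tail of the PFS curve.

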13.8 Analysis of Correlative Biomarkers

Paired pre- and post-treatment biopsies will be obtained when available in consenting participants. We will explore the relationship between integrated biomarkers PDL1/PD1/PD2 status (PDL1 status, PDL1 in infiltrating lymphocytes, PD2 status in archival tumor) and the absence of disease progression to combination treatment eribulin and pembrolizumab. We will use Fisher's Exact Test to assess the relationship between each biomarker and the absence of

disease progression to combination treatment. Each is expected to have similar characteristics. For example, with this design, assuming tissue is available on 90% of the sample, the probability of concluding combination treatment eribulin and pembrolizumab response is related to the exploratory biomarker is 82%; given the unknown true response is 65% and 4% in positive marker versus negative marker participants, respectively, assuming 45% of the population is over-expressed for PDL1. The power to detect the relationship of interest increases as the prevalence of the biomarker increases. The operating characteristics of this design are calculated using a two-sided exact test with 10% type I error.

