13. STATISTICAL CONSIDERATIONS

13.1 Study Design/Endpoints

We have designed a single stage phase II, three-arm study for the primary endpoint of progression-free rate at 12 weeks. Participants will be stratified among three-arms based upon participant diagnosis. Arm A will consist of leiomyosarcoma participants. Arm B will consist of liposarcoma participants. Arm C will consist of undifferentiated pleomorphic sarcoma/other sarcomas.

The primary endpoint is the 12-week progression-free survival. The progression-free survival is defined as the absence of disease progression at 12 weeks from study enrollment. Participants without stable disease or complete or partial response, with deaths of any cause within 12 weeks, with progression within 12 weeks, or without confirmatory scans at 12 weeks' post baseline evaluation will be counted as failures. We will enroll 19 participants in each arm following a single stage approach.

Toxicity is an important secondary endpoint. With 19 participants in each arm, there is at least 86% probability of observing one or more toxicities with a true rate as low as 10%. With 19 treated participants in each arm, the maximum width of a 90% two-sided confidence interval for any estimated adverse event proportion is $\pm 20\%$.

Progression-free survival (PFS) and overall survival (OS) of participants receiving combination therapy will be described using the method of Kaplan and Meier and 90% confidence intervals for PFS and OS will be reported.

NOTE: With Protocol Version 15MAY2024, further long-term follow-up is being terminated.

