13.2 Sample Size, Accrual Rate and Study Duration

Arm A (Leiomyosarcoma)

We will assess the progression-free rate at 12 weeks (null: 30%, alternative: 60%). We will need to observe at least 9 participants absent of disease progression out of 19 participants to accept the treatment. The overall power for the progression-free rate at 12 weeks is 91% using the exact binomial distribution. The operating characteristics of this design are calculated using a one-sided exact test with 10% type I error.

Arm B (Liposarcoma)

We will assess the progression-free rate at 12 weeks (null: 30%, alternative: 60%). We will need to observe at least 9 participants absent of disease progression out of 19 participants to accept the treatment. The overall power for the progression-free rate at 12 weeks is 91% using the exact binomial distribution. The operating characteristics of this design are calculated using a one-sided exact test with 10% type I error.

Arm C (Undifferentiated Pleomorphic Sarcoma/Other Sarcomas)

We will assess the progression-free rate at 12 weeks (null: 30%, alternative: 60%). We will need to observe at least 9 participants absent of disease progression out of 19 participants to accept the treatment. The overall power for the progression-free rate at 12 weeks is 91% using the exact binomial distribution. The operating characteristics of this design are calculated using a one-sided exact test with 10% type I error. Additionally, response to individual sarcomas histologic subtypes will be reported descriptively.

Table 10. Accrual Targets

Accrual Targets				
Ethnic Category	Sex/Gender			
	Females		Males	Total
Hispanic or Latino	1	+	1	= 2
Not Hispanic or Latino	27	+	28	= 55
Ethnic Category: Total of all participants	28	+	29	= 57
Racial Category				
American Indian or Alaskan Native	1	+	1	= 2
Asian	1	+	1	= 2
Black or African American	1	+	1	= 2
Native Hawaiian or other Pacific Islander	1	+	1	= 2
White	24	+	25	= 49
Racial Category: Total of all participants	28	+	29	= 57

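### Section 13.8 says biomarker power rises with prevalence, but it peaks near the assumed 45%; the 82% is a per-cohort figure whose inputs imply an overall rate near the 30% null

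*Combined protocol and SAP*

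**What the plan says.** Section 13.8 plans one test per marker: "We will use Fisher's Exact Test to assess the relationship between each biomarker and the absence of" disease progression. It gives one worked power figure, 82%, for a two-sided exact test at the 10% level. The conditions are "assuming tissue is available on 90% of the sample", "given the unknown true response is 65% and 4% in positive marker versus negative marker participants, respectively", and "assuming 45% of the population is over-expressed for PDL1". It then states: "The power to detect the relationship of interest increases as the prevalence of the biomarker increases". It also says that the other markers should behave similarly, which extends the 82% to them.

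The sample size is in section 13.1: "We will enroll 19 participants in each arm following a single stage approach". Section 13.2 sets the same hypotheses for every arm, a 30% null and a 60% alternative: "We will assess the progression-free rate at 12 weeks (null: 30%, alternative: 60" percent). Sections 1.1 and 13.9.2 say that the cohorts are analysed separately. No pooled or stratified marker test is planned.

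**The concern.** Two things look wrong. First, the power of a two-group comparison depends on both groups being reasonably filled. As marker-positive patients become the large majority, few marker-negative patients remain and power must fall, so a statement that power always rises with prevalence cannot hold.

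Second, 4% in the marker-negative majority pulls the overall rate down so far that the example may not describe a cohort in which the regimen works as section 13.2 hopes. Section 9.2.1.1 treats PD-L1 as an integrated marker that may serve as a stratification variable in later trials. A reader who takes 82% as a general property of the design could read a non-significant result in a successful cohort as well-powered evidence against an association.

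**Working it through.** **Inputs.** 19 per arm (13.1). Tissue on 90%, so 0.90 × 19 = 17.1, taken as n = 17. Rates p₁ = 0.65 (positive) and p₀ = 0.04 (negative), prevalence π = 0.45, Fisher's exact test, two-sided 10% (all 13.8). Null 30%, alternative 60%, success at 9 or more of 19 (13.2). Assumption: the number of marker-positive patients is Binomial(17, π).

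**Step 1: reproduce the 82%.** Power = Σₖ Bin(k; 17, π) Σₐ Σ_b Bin(a; k, p₁) Bin(b; 17 − k, p₀) × 1[Fisher p ≤ 0.10]. Full enumeration gives 81.9%, which matches. With n = 18 it is 84.8% and with n = 19 it is 87.7%. With all three cohorts pooled (51 samples, split 23/28) it exceeds 99.9%. The stated figure is therefore a single-cohort figure.

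**Step 2: vary prevalence only (n = 17, 65% versus 4%).**

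| Prevalence | Power |
|---|---|
| 20% | 63.3% |
| 30% | 76.6% |
| 40% | 81.6% |
| 45% | 81.9% |
| 50% | 81.1% |
| 60% | 76.1% |
| 70% | 65.9% |
| 80% | 47.5% |
| 90% | 18.8% |

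The maximum is at about 44%. The assumed 45% is already at the peak.

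**Step 3: overall rate implied by the example.**
- 0.45 × 0.65 + 0.55 × 0.04 = 0.2925 + 0.0220 = 31.5%.
- At 31.5%, the chance of 9 or more successes in 19 is 10.8%, against 8.4% at 30% and 91.2% at 60%.
- Ceiling with 4% in negatives and 45% prevalence: 0.45 × 1 + 0.022 = 47.2%.
- Positive-group rate needed for 60% overall: (0.60 − 0.022)/0.45 = 128%, which is impossible.
- Prevalence needed for 60% overall at 65% versus 4%: (0.60 − 0.04)/(0.65 − 0.04) = 92%. Step 2 shows that power is already down to 18.8% at 90%.

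**Step 4: power when the rates average 60% (π = 0.45).** Set p₀ = (0.60 − 0.45 p₁)/0.55. The last column is an exact conditional test stratified by cohort, 3 × 17 samples, two-sided 10%, from 20,000 simulated trials with random marker splits and the same pair in each cohort.

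| p₁ / p₀ | One cohort, Fisher | Three cohorts, stratified |
|---|---|---|
| 65% / 55.9% | 5.9% | 13.5% |
| 70% / 51.8% | 10.2% | 31.2% |
| 75% / 47.7% | 18.2% | 56.4% |
| 80% / 43.6% | 30.2% | 80.7% |
| 85% / 39.5% | 46.0% | 94.6% |
| 90% / 35.5% | 64.2% | 99.2% |

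Two further single-cohort cases carry over the effect in the plan's example. Keeping the 61-point difference (93.6% versus 32.6%) gives 77.0%. Keeping the odds ratio, (0.65/0.35)/(0.04/0.96) = 44.6, gives 95.3% versus 31.1% and power of 82.9%.

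**The case against.** The best defence is that section 13.8 offers an example with rates it calls unknown, in an analysis it describes as exploration. An example in which benefit is confined to marker-positive patients need not equal the primary alternative, and the 82% is right for its inputs. That stands: a reader might infer that the 82% is a calculation error, and it is not. The only outright error is the prevalence sentence, and even that holds up to about 45%.

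The word response is also ambiguous. The test in 13.8 names absence of progression as its outcome, but the 65% and 4% are called response, and section 1.3 lists objective response as a separate endpoint. A 31% objective response rate is compatible with 60% progression-free. The conflict in Step 3 therefore depends on reading response as absence of progression. Under the other reading, the power figure would be for a different outcome from the one the test names, so the wording needs correction either way.

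A reader might further infer that marker power must be far below 82% whenever a cohort succeeds. The documents do not support this. They fix no effect size at a 60% average, and keeping the example's odds ratio loses nothing. Nor does passing 9 of 19 require a true rate of 60%.

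Finally, a reader might infer that pooling the cohorts would recover most of the lost power. That depends on the contrast. Measured against 81.9%, pooling recovers (13.5 − 5.9)/(81.9 − 5.9) = 10% of the gap at 65% versus 56%, and 29% at 70% versus 52%. It recovers more than half only from a difference of roughly 27 points. It also assumes a common odds ratio, which sits uneasily with the histology-specific rationale in section 2.1 and with the separate-by-cohort rule.

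**Conclusion.** The point holds in limited form. The prevalence sentence is false as a general statement under the section's own inputs: power falls from 82% near 45% prevalence to 76% at 60% and 48% at 80%. This rests only on n = 17 and a binomial marker split, the combination that reproduces the plan's figure.

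The 82% is correct but applies to one cohort with an overall rate of 31.5%. If the outcome is absence of progression, the example cannot describe a cohort at the 60% alternative. There, at 45% prevalence, per-cohort power lies between 6% and 83% for the pairs examined, and reaches about 82% only for contrasts near 95% versus 31%.

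Severity is minor. The marker analyses are correlative, later use of PD-L1 for stratification is only a possibility, and nothing in the primary decision changes. Misreading of a null result is a risk, not something the documents show will happen.

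**What to change.** In section 13.8:

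1. Delete the prevalence sentence, or limit it to prevalences below about 45% under the stated inputs.
2. State that the 82% is for a single cohort of about 17 samples, and that the outcome is absence of progression at 12 weeks if that is what is meant.
3. Replace or supplement the 65% versus 4% example with a short table of power over a range of prevalences and over rate pairs compatible with the 60% design rate, such as those in Step 4.
4. Optionally, add a cohort-stratified exact test across the three arms (about 51 samples) as a supportive analysis. This needs an explicit exception to sections 1.1 and 13.9.2 and a stated common-odds-ratio assumption. It raises power from 18% to 56% at 75% versus 48%, and from 30% to 81% at 80% versus 44%, but reaches only about 14% at 65% versus 56%.

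The cost is wording and a re-run power calculation, with no extra patients or tissue. The downside is that the stated power becomes less favourable.
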